We describe all study measures in detail in the study design and procedures sections below and they appear in our appendices. Below is a brief summary of assessments. Purchasing Survey: After obtaining permission from caregivers, a survey will be administered to students after they have made a food or beverage purchase at a school store. The survey will assess participants nutrition knowledge and label awareness, recall, and use, and trust in label information. Frequency of school store visits and sociodemographic characteristics (e.g., age, sex, race/ethnicity, grade level, and height and weight) will also be assessed (see Appendix B for survey). Beverage Frequency Questionnaire: Participants will also complete a beverage frequency questionnaire to assess their consumption of different types of beverages. This questionnaire will be based on the BEVQ-15, a survey instrument that has been validated as an effective tool used to capture changes in beverage consumption. (1-4) (see Appendix E for BEVQ-15). For each beverage category, the questionnaire assesses frequency of consumption and volume typically consumed. (see Appendix D for adapted questionnaire).

Group Modifications

Describe necessary changes that will or have been made to the study instruments for different groups.

None of the survey questionnaires will differ across randomly assigned groups. Regarding the schools that will be enrolled in the study, pairs of matched private/public schools will be randomized to 1 of 3 labeling conditions

Method for Assigning Subjects to Groups

Describe how subjects will be randomized to groups.

Individual participants will not be randomly assigned to groups. Instead, randomization will occur at the school level. Nine schools will be participating in this research and randomization will be stratified based on whether a school is public (n = 6) or private (n = 3). The Penn research team will use a random number generator to randomize schools to one of three labeling conditions, and the Guatemala team will implement the labels based on the randomization assignment.

Administration of Surveys and/or Process

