Students and their caregivers will first be contacted about study participation using a permission letter (see Appendix A) sent either as a printed letter or electronically. The letter will explain that their children may be asked to complete a short survey after making a purchase at the school store. Caregivers who wish to refuse participation can call a number provided in the permission letter. A list will be maintained with the names of students who have permission to participate. Research assistants will consult this list before administering any surveys to ensure the student has permission to participate. Adolescents who consent to participate and have made a purchase from the school store will be given the opportunity to complete a short survey; verbal assent must be obtained prior to enrollment. Research assistants will be stationed at the school stores during the heaviest traffic times (between 10:00am and 1:30pm and 2:30pm and 3:30pm) Monday to Friday and will invite adolescents to participate in the survey after they make a food and/or beverage purchase at the school store. Research assistants will record the item purchased (type of food/beverage) along with brand, quantity, size, and price. In addition, we will administer a survey that includes a validated beverage frequency questionnaire to assess typical beverage intake (Appendix B). Research assistants will also record the number of students who refuse participation along with their gender. The survey is estimated to last approximately 5-10 minutes. Participants will only be eligible to take the survey once.

Data Management

Describe how and who manages confidential data, including how and where it will be stored and analyzed. For instance, describe if paper or electronic report forms will be used, how corrections to the report form will be made, how data will be entered into any database, and the person(s) responsible for creating and maintaining the research database. Describe the use of pseudonyms, code numbers and how listing of such identifiers will be kept separate from the research data.

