
Study duration

We anticipate it will take the entirety of the six week data collection period to survey all 1500 adolescents. It will take 5-10 minutes for each participant to complete the survey. We aim to implement the warning labels in school stores by May 2018 and will complete the data collection by the end of June 2018.

Resources necessary for human research protection

Describe research staff and justify that the staff are adequate in number and qualifications to conduct the research. Describe how you will ensure that all staff assisting with the research are adequately informed about the protocol and their research related duties. Please allow adequate time for the researchers to conduct and complete the research. Please confirm that there are adequate facilities for the research.

Characteristics of the Study Population

Target population

To be eligible for the survey component of this project, participants must be: 1) Between 12-18 years or older; 2) Be a currently enrolled student at one of the enrolled schools 3) Have made a purchase at the school store.

Subjects enrolled by Penn Researchers

0

Subjects enrolled by Collaborating Researchers

1500

Accrual

The schools participating in this study will enable us to easily recruit students shopping at the school stores. With a sample size of 1500 (500 per labeling condition), this study is powered to detect small mean differences between the conditions. Specifically, if all three conditions differ by only .21 standard deviations, there is an 82% chance that we would find all differences to be significant.

Key inclusion criteria

To be eligible for the survey component of this project, participants must be: 1) Between 12-18 years or older; 2) Be a currently enrolled student at one of the enrolled schools 3) Have made a purchase at the school store.

Key exclusion criteria

Individuals not meeting the inclusion criteria above will be excluded. Those who will not or cannot give assent will also be excluded from the study. No one will be excluded on the basis of sex or race

Vulnerable Populations

Children Form

Pregnant women (if the study procedures may affect the condition of the pregnant woman or fetus) Form

Fetuses and/or Neonates Form

Prisoners Form

Other

None of the above populations are included in the research study

The following documents are currently attached to this item:

Vulnerable Populations (inclusionofchildren.doc)

Populations vulnerable to undue influence or coercion

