include 100% juice). Frequencies and percentages will be used to describe categorical variables such as percent of students purchasing a sugary drink. Medians and interquartile ranges will be reported for continuous variables that exhibit skewness. Data will be descriptively summarized overall and by labeling strategy. All outcomes will be analyzed at the purchase level. The mean volume of sugary drinks at each two-week period will be modeled among the calorie label, text label, and graphic label arms by a linear regression model including intervention arm, two-week period, interactions of period and intervention arm and type of school (private or public) as independent variables. We will conduct exploratory analyses to examine whether usual frequency of sugary drink intake (high versus low) and biological sex moderate label effects. Examining only aggregate sales data could lead to incorrect inferences. Therefore, complementary individual-level survey data on purchases will also be collected. This aggregate/individual-level data combination will improve inferences about label effects. Although stratification by school type guarantees this variable will be balanced across our intervention arms, we are including it as a covariate in the model because it will enhance the precision of estimating intervention effects, as it explains variability in the outcome. The effectiveness of the interventions will be tested by evaluating the null hypothesis that the coefficients of the interactions of period and intervention are 0, indicating no change in the difference in volume of sugary beverages purchased across intervention arms from baseline. To account for clustering of purchases within schools, test statistics will be corrected using the variance inflation factor (VIF) as determined by the estimated intraclass correlation coefficient (ICC) for within school correlation. Primary and secondary outcomes in the calorie, text-based warning label, and graphic warning label arms will each be compared to one another. A Bonferroni-holm correction will be applied to control for multiple comparisons. We do not expect substantial missing data due to the point-of-sale technology we are using. The primary analysis will examine changes in labeled (sugary) and non-labeled beverages. Secondary analyses will examine changes for the following specific beverage categories: sugar-sweetened cola, sugar-sweetened sports drinks, sugar-sweetened lemonades/iced teas/juices, artificially-sweetened drinks (e.g., Diet Coke), milk, 100% fruit juice, unsweetened coffee/tea, and bottled water. For the survey data, we will conduct similar linear regression analyses to compare total mean kcals purchased among intervention arms.

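### The 82% power at 0.21 SD matches 1,500 independent students; with nine randomised schools it holds only if the school ICC is close to zero

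*Protocol*

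**What the plan says.** The only power statement in the two documents is in the Protocol, Accrual: "With a sample size of 1500 (500 per labeling condition), this study is powered to detect small mean differences between the conditions". It continues that "if all three conditions differ by only .21 standard deviations, there is an 82% chance that we would find all differences to be significant". No ICC, design effect, alpha or sidedness accompanies it, and the number of schools does not enter it.

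Other parts of the Protocol describe a clustered design:

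- Method for Assigning Subjects to Groups: "Individual participants will not be randomly assigned to groups. Instead, randomization will occur at the school level". Nine schools take part, six public and three private, stratified by type.
- Analysis Plan: "All outcomes will be analyzed at the purchase level". Also: "To account for clustering of purchases within schools, test statistics will be corrected using the variance inflation factor (VIF"), with the VIF taken from the estimated within-school ICC. The arms are compared pairwise, and "A Bonferroni-holm correction will be applied to control for multiple comparisons".
- Analysis Plan, on the survey: "For the survey data, we will conduct similar linear regression analyses to compare total mean kcals purchased among intervention arms".
- Administration of Surveys and/or Process: "Participants will only be eligible to take the survey once".
- Design: recruitment is stratified so that about 750 of the surveyed students attend public schools and 750 attend private schools.

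The Secondary outcome variable(s) section makes survey-based kilocalories a secondary outcome; the primary outcome comes from sales data. The SAP has no sample-size section. Its Description of data confines the primary analysis to two randomised schools, one per condition.

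**The concern.** The analysis plan expects purchases within a school to be correlated and will penalise the test statistics for it. The power figure appears to include no such penalty. With well over 100 surveyed students per school, even a very small ICC produces a material design effect, so the stated power and the planned test may be far apart.

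A reader who trusts the 82% could take a null survey result as evidence against small label effects when the design had little chance of showing them. The sentence could also be read as covering the primary outcome, although 1,500 students is the size of the survey and not of the sales data.

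**Working it through.** **Inputs from the Protocol.** 500 students per arm; spacing 0.21 SD; three pairwise comparisons with Holm; nine schools; half the students public and half private.

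**Assumptions.** Overall alpha 0.05, two-sided unless noted. Arm means 0, 0.21 and 0.42 SD, the natural reading of three conditions each differing by 0.21. Normal critical values. An even split of one private and two public schools per arm. ICCs from 0 to 0.05, since the documents give none. All-three powers come from 2,000,000 simulations.

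**Step 1: reproduce the 82% with independent students.**

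- One pair: SE = √(2/500) = 0.0632 and 0.21/0.0632 = 3.320. At two-sided 0.05/3 the critical value is 2.394, so power = Φ(3.320 − 2.394) = 82.3%.
- All three significant: 82.6–82.7% unadjusted and 82.5–82.6% with Holm. Holm costs almost nothing here because its binding condition for rejecting all three is that the largest p-value is below 0.05.
- Readings that do not match: one unadjusted pair at two-sided 0.05, 91.3%; all three with plain Bonferroni, 65%; all three at one-sided 0.05, 90.6%.

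Both two-sided readings that match contain no design effect. All three at one-sided 0.05 comes down to 82% at a VIF of about 1.24, an ICC of about 0.0013.

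**Step 2: design effect.** The private half gives 750/3 = 250 students per private school. The public half gives 750/6 = 125 per public school. The weighted cluster size per arm is (250² + 2 × 125²)/500 = 187.5, so VIF = 1 + 186.5 × ICC and the effective n per arm is 500/VIF.

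**Step 3: power at 0.21 SD.** The last column is the spacing that restores about 82% all-three power, 0.21 × √VIF.

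| ICC | VIF | Effective n per arm | All three, Holm, two-sided | One pair at 0.05/3 | All three, Holm, one-sided | Spacing (SD), two-sided |
|---|---|---|---|---|---|---|
| 0 | 1 | 500 | 83% | 82% | 91% (unadjusted) | 0.21 |
| 0.001 | 1.187 | 421 | 72% | 74% | 84% | 0.229 |
| 0.002 | 1.373 | 364 | 62% | 67% | 76% | 0.246 |
| 0.005 | 1.933 | 259 | 37% | 50% | 55% | 0.292 |
| 0.01 | 2.865 | 175 | 15% | 33% | 30% | 0.356 |
| 0.02 | 4.73 | 106 | 4% | 19% | 11% | 0.457 |
| 0.05 | 10.325 | 48 | 0.4% | 9% | 2% | 0.675 |

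Simulating the nine school means directly gives the same two-sided all-three figures: 72, 62, 36, 15, 4 and 0.4%. Equal schools of 1,500/9 ≈ 167 students change little: 73, 64, 41, 18, 5 and 0.5%.

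**Step 4: break-even ICC for all-three power with Holm.**

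- Two-sided: 80% is lost at VIF 1.048, ICC 0.048/186.5 ≈ 0.0003. 50% is lost at VIF 1.610, ICC 0.610/186.5 ≈ 0.003.
- One-sided: 80% is lost at VIF 1.285 (ICC about 0.0015) and 50% at VIF 2.073 (ICC about 0.006).

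**The case against.** The strongest reply is that no test is invalid. The VIF correction is already planned, the remedy is wording only, and the sentence concerns a secondary survey outcome in a nine-school design that the SAP no longer analyses. That is true, but the correction protects the error rate and lowers power, so it widens the gap from 82%. That the figure does not carry over to the SAP's analysis is a further reason to qualify it.

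Four narrower points deserve weight.

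- **No ICC is given.** The documents therefore cannot show what value is realistic. The relevant ICC is also the one left after school type, which is a stratification factor and a model covariate, and the Protocol expects similar student demographics within each type. This stands. It could make the ICC smaller, but nothing in the documents supports a value below 0.001.
- **The 82% may be a pairwise figure.** Power then falls less steeply, as the table shows. The most generous readings, one unadjusted pair, reach 82% at VIF 1.33 two-sided (ICC about 0.002) or 1.68 one-sided (ICC about 0.004). These limits are still very small.
- **Survey timing is unclear.** Design places the survey in the intervention weeks, whereas Study duration spreads it over all six weeks. On the second reading the table would not apply as it stands. Nor would the 82%, because not all 500 students per arm would be surveyed while labels were displayed.
- **The VIF sentence names purchases.** For the survey it is only implied, through the purchase-level statement and the similar regressions. Since each student is surveyed once, surveyed purchases cluster by school just as students do.

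**Conclusion.** The concern holds. The arithmetic behind the 82% is correct for 500 independent students per arm, but that is not the design described. On the all-three, two-sided reading with Holm, power drops below 80% once the school ICC exceeds about 0.0003 and below 50% once it exceeds about 0.003. Every more favourable reading examined still needs an ICC of about 0.004 or less to reach 82%.

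The size of the loss rests on the assumed ICCs, alpha 0.05, normal critical values and an even split of schools. It applies to a cross-sectional comparison of surveyed students across arms. It does not apply to the sales-based period-by-arm interaction, where stable school effects would partly cancel. The 82% describes neither that test nor the SAP's two-school analysis. As the only power statement supplied, it should be corrected before anyone relies on it.

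**What to change.** Restate the Accrual sentence; do not enlarge the trial.

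1. Give alpha, sidedness, how multiplicity enters the calculation, the number of schools and the students per school.
2. State a planning ICC range with its source, conditional on school type if that is what the model uses, and report power or detectable spacing with the VIF. On the basis above (two-sided 0.05, Holm), about 82% power for all three differences needs a spacing of about 0.23, 0.29, 0.36, 0.46 and 0.67 SD at ICCs of 0.001, 0.005, 0.01, 0.02 and 0.05. Checked by simulation, these rounded spacings give 82–84%.
3. Say that the figure concerns survey outcomes in the nine-school, three-arm design, and that it does not cover the sales-based primary outcome or the SAP's two-school primary analysis.
4. Remove or qualify the claim that the study is powered for small mean differences.

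The cost is wording and a less favourable stated figure; no planned analysis changes.

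A separate, optional point: the Analysis Plan names no reference distribution for the corrected statistics. If a t distribution with 9 − 3 − 1 = 5 school-level degrees of freedom were used, all-three power at 0.21 SD would be about 58% unadjusted and 55% with Holm even at ICC 0. The spacing needed with Holm would then be about 0.266 × √VIF.

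### The 82% power statement leaves out the pattern of means it needs and holds only if students are independent, which the school-randomised design does not provide

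*Protocol*

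**What the plan says.** The power statement is in the protocol under Accrual. It opens "With a sample size of 1500 (500 per labeling condition"), claims that "this study is powered to detect small mean differences between the conditions", and then gives the figure: "if all three conditions differ by only .21 standard deviations, there is an 82% chance that we would find all differences to be significant". It names one effect size. It does not give the three assumed means, alpha, sidedness, an ICC or a design effect, or the outcome to which it applies.

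Three other parts of the protocol bear on it:

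- Analysis Plan, comparisons: "Primary and secondary outcomes in the calorie, text-based warning label, and graphic warning label arms will each be compared to one another". With three arms, that is three pairwise tests.
- Analysis Plan, multiplicity and clustering: "A Bonferroni-holm correction will be applied to control for multiple comparisons", and "To account for clustering of purchases within schools, test statistics will be corrected using the variance inflation factor (VIF") derived from the estimated ICC.
- Method for Assigning Subjects to Groups: schools, not students, are randomised, nine in all.

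The SAP contains no power calculation, so nothing there completes or replaces the statement.

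**The concern.** If conditions A and B differ by 0.21 SD, and B and C also differ by 0.21 SD, then A and C differ by either 0 or 0.42 SD. Three pairwise differences of 0.21 SD cannot exist together. The sentence therefore needs an assumption that it does not state, and its 82% depends heavily on what that assumption is.

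The figure is also an individual-level calculation, as the reproduction below shows, while the design randomises schools and the analysis is to be deflated for within-school correlation.

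This is the only justification of the 1500 students in either document. Someone relying on it would conclude that a spread of 0.21 SD across the three labels is detectable in every comparison, including graphic against text, which the Objectives section names as a question of interest. They would also take 82% to be the power of the trial as designed.

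**Working it through.** **Inputs.** From Accrual: n = 500 per condition, difference 0.21 SD (SD = 1), stated power 82% for all differences. From the Analysis Plan: three pairwise comparisons with Holm. From Method for Assigning Subjects to Groups: nine schools. Assumed here because the documents do not give them: family-wise alpha 0.05, two-sided; ICC.

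**1. One pair.** For two arms, power ≈ Φ(δ·√(n/2) − z), where z is the two-sided critical value. With δ = 0.21, δ·√250 = 3.320.

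- At 0.05: Φ(3.320 − 1.960) = 91.3%.
- At 0.05/3: Φ(3.320 − 2.394) = 82.3%.

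**2. Reproducing 82% as all-differences power.** Take means 0, 0.21 and 0.42. The 0.42 SD pair is almost certain to be significant (power above 99.99%), so the question is whether both adjacent pairs succeed. Each fails with probability 1 − 0.913 = 0.087. The two adjacent contrasts share the middle arm with opposite sign (correlation −0.5), so they rarely fail together. The joint probability is therefore close to 1 − 2 × 0.087 ≈ 0.826. Simulation with 1,000,000 replicates and pooled variance agrees: 82.6% unadjusted and 82.5% with Holm. Plain Bonferroni would give 65.0%.

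The stated 82% is thus reproduced in two ways:

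| Route | Result | What it is |
|---|---|---|
| Means 0/0.21/0.42, Holm | 82.5% | Chance that all three differences are significant; outer pair 0.42 SD apart |
| One 0.21 SD pair at 0.05/3 | 82.3% | Power of a single comparison |

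The documents do not show which was used.

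**3. If 0.21 SD is the whole spread.** With means 0, 0.105 and 0.21, each adjacent pair has δ·√250 = 0.105 × 15.81 = 1.660 and power Φ(1.660 − 1.960) = 38%. Both adjacent pairs must succeed, and their tests are negatively correlated. Simulation gives 7.3% unadjusted and 6.3% with Holm.

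**4. Clustering.** With 1500/9 ≈ 167 students per school, the design effect is 1 + (166.7 − 1) × ICC. Each test statistic is divided by its square root. For means 0/0.21/0.42 with Holm (the range covers normal and t reference distributions):

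| Assumed ICC | Design effect | All-differences power | One 0.21 SD pair at 0.05/3 |
|---|---|---|---|
| 0 | 1.00 | 82.5% | 82.3% |
| 0.001 | 1.17 | 73–74% | 75% |
| 0.005 | 1.83 | 40–41% | 52% |
| 0.01 | 2.66 | 18% | 36% |

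The last column is Φ(3.320/√(design effect) − 2.394). At ICC 0.005, for example, 3.320/√1.828 = 2.456 and Φ(0.062) = 52%. The table assumes equal school sizes and a known ICC.

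**The case against.** The strongest reply is that the number is right. Read in the ordinary way, the sentence says that neighbouring conditions are 0.21 SD apart, or that every pair differs by at least that much. Three ordered means with that minimum gap are 0, 0.21 and 0.42. This gives 82.5% under the protocol's own Holm rule, and the wording about all differences fits all-pairs power. This stands. A reader might infer that 82% is a miscalculation resting on an impossible scenario, but the documents do not support that: a possible scenario produces the figure, and what is missing is the statement of it. Nor can one say that 82% arises only with a 0.42 SD outer difference, because the single-pair route produces it without one.

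It would also be unfair to cite the roughly 3% obtained when two arms are equal and one differs by 0.21 SD. The sentence supposes that all three conditions differ, and with two equal arms the third rejection would be a false positive.

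The reply continues that the consequence is limited. The 1500 are survey respondents, while the protocol's primary outcome comes from sales data. The SAP's primary analysis compares posters with control in two schools and involves no three-arm test. This also stands: correcting the sentence changes no planned analysis.

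None of it answers the clustering point. The adjacent-gap reading matches 82% only with 500 independent students per arm. The protocol describes its variance correction for purchases within schools and plans similar regressions for the survey data, and students surveyed in the same school share an assigned label in any case.

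**Conclusion.** The point holds as a defect of statement and of design allowance, not as an arithmetic error. The figure of 82% is correct for either of two calculations, but the sentence describes neither fully. Read as all-differences power, it conceals a 0.42 SD outer difference. Read as single-pair power, its reference to all differences is wrong. If 0.21 SD is the full, equally spaced spread, the chance of finding all three differences is about 6–7%.

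On either route, the design does not deliver 82% for any positive within-school correlation once the planned correction is applied. All-differences power of 82.5% becomes about 73–74%, 40–41% and 18% at ICCs of 0.001, 0.005 and 0.01. These ICCs are illustrations, not estimates; the size of the loss depends on a value that the documents do not give. The results also rest on assumed two-sided 0.05 and about 167 students in each school. The conclusion concerns the protocol's power claim and does not show that any planned analysis is invalid.

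**What to change.** Rewrite the Accrual sentence so that it:

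- gives the assumed means (0, 0.21 and 0.42 SD), and so discloses the 0.42 SD outer difference;
- states alpha, sidedness and the Holm rule;
- names the outcome to which the power applies;
- labels 82% as the power to find all three differences if students were independent;
- reports the lower power after the planned variance inflation correction over a stated ICC range, with the source of that range.

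If the figure was in fact derived as one comparison at 0.05/3, the sentence should say so and drop the reference to all differences.

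The cost is a few sentences and a short calculation. Enrolment, randomisation and the planned tests are unchanged. Stating the pattern of means leaves 82% as it is under independence. The clustering allowance is what makes the stated power less favourable, and the general claim about small differences should then be qualified to match.
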